2.3 Project design

The study is a human research study in which customers that are taking the collagen activator from Avea are observed for six months. The trial is in the form of a post marketing surveillance observational trial since the product has already been approved and is sold on the market. All participants are voluntarily taking the collagen activator. There is no blinding, randomization or placebo control that is taking place in the trial. The results are compared individually for each participant after the follow ups from their baseline measurements.

- The trial exposure is the Collagen activator from Avea
 - Potential participants are contacted after purchasing the collagen activator for 6 months via Avea's online shop. After successful recruitment they undergo the baseline assessment. They are instructed to only start taking the collagen activator once the baseline assessment is completed.
 - o Daily oral intake of 1 package of 11.5g diluted in water over six months, taken in the morning
- Saliva samples are taken twice (time points 0 and +6 months) to determine biological age via epigenetic methylation clock (Trume labs are the test providers and analysers)
- Skin analysis takes place at time points 0, +1 and +3 months to determine skin quality. This includes measurements of hydration, elasticity, skin thickness and density, as well as pigmentation, wrinkles, texture, UV-spots, pores, redness and porphyrins.
- Skin tests used for this are the corneometer, cutometer, ultrascan and Visia scan.
- Every month the participants receive a questionnaire regarding recent subjective changes, adverse reactions and adherence

The individual duration expected for each patient from the recruitment process onwards is about 6-7 months

- The goal is to recruit 60 healthy participants that are older than 35 years and are voluntarily taking the collagen activator for 6 months
- 2-3 weeks from being recruited to receiving a date for the baseline measurements
- Day 1 being the day of the baseline measurements
- Follow ups for the skin measurements take place +1 and +3 months from day 1
- Follow up for the saliva test takes place +6 months from day 1

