At the first visit at the Dermatology clinic Hautwerk (time point 0), the medical professional will then check if the participant has already filled out the medical questionnaire. If yes, they will go through the most important points to check the participant understood everything correctly, if no, they will supervise the participant in filling out the questionnaire. After the questionnaire is completed, the medical professional will instruct the participant to take a saliva sample via spitting on a spoon and transferring the saliva to a piece of paper (provided by TruMe laboratories). The paper has to dry for 45 minutes in the open air (taken care of by the medical professional). Then, the medical professional performs the non-invasive skin scan (Visia analysis system), and the tests with the corneometer, cutometer and ultrascan. Afterwards, there will be time for the participant to rest until it can be sure that there are no adverse reactions to any of the procedures performed. The whole visit will be recorded by the medical professional. The total visit should take between 30 to 60 minutes. The saliva samples are stored without risk at ambient temperature. The study personnel will collectively ship the samples to Trume labs once all the baseline visits are completed.

Specifics to the skin measurement procedures:

- Cutometer: The cutometer is a non-invasive device that measures the elasticity of the skin. It uses suction to apply a negative pressure on the skin, which causes the skin to deform. The device then measures the time it takes for the skin to return to its original position after the suction is released. This measurement is known as the skin's viscoelastic properties, and it is used to assess the skin's firmness and elasticity.
- 2. Corneometer: Corneometer is a non-invasive device that measures the moisture content of the skin. It works by applying a small electrical current to the surface of the skin, which measures the skin's electrical impedance. The device then calculates the moisture content of the skin based on the electrical impedance. This measurement is used to assess the hydration level of the skin.

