- After the determination of biological age, the sequence data is deleted and the saliva samples are destroyed. This minimizes the risks of the data being used in any other way or of personal genetic information being revealed.
- The samples are screened upon arrival at Trume labs and in the case that a sample is contaminated or too wet, we will be informed and ask the participant to retake the saliva sample. As we ship the samples every week, in the case that a sample is contaminated it will be possible for the participant to redo the sample within 1 to 1.5 months maximum considering shipping times. The delay of the datapoint will be taken into account for the analysis.

•

Questionnaire

- The private information provided in the questionnaires will be kept confidential, following our protocol for data protection
- Contact details of trial doctor's are provided to the patients for any case of privacy concerns, mental support or language difficulties

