- Upon receiving the sample, it undergoes a visual inspection to ensure it is not contaminated or too wet.
- If the sample passes the visual inspection, DNA extraction and bisulfite conversion are performed to differentiate the methylated and unmethylated DNA.
- Small regions of DNA are extracted and sequenced to quantify a percentage of DNA methylation.
- Independent laboratory services are used to perform all sequencing procedures.
- Personally identifiable information is not provided to TruMe, they only receive encrypted information to ensure confidentiality.
- Multiple layers of encryption are used to protect the data.
- TruMe never provides your information to your employer or health insurance company.
- Individual-level information is not shared with any third party without explicit consent.
- Information is only provided to law enforcement if required to comply with a valid subpoena or court-ordered request.

Processes in place to ensure traceability of biological material:

- Upon receiving the sample, it is scanned into an internal registration system.
- The laboratory sends the resulting data to TruMe along with the barcode that came with the sample.

• TruMe does not receive personal identifiable information for participants of this study. Storage and technical requirements to be met:

• The laboratory maintains a cooling system to ensure appropriate storage of biological material.

Shipping biological material or data collected during the research project outside the research site:

- the receiver address: TruMe, Inc., [name]
- responsible person to whom materials or data are sent: [name]
- purpose of shipment: Analysis of saliva samples to get biological age
- temperature control: not necessary, stable at ambient temperatures
- participant confidentiality is guaranteed via separating Personally identifiable information (PII) and personal health information (PHI).
- Participants are being sufficiently informed and consent is obtained that their biological material is being sent to the US to the contracted laboratory (Trume labs) that performes the analysis of the saliva samples.

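### A rejected month-0 saliva sample may be retaken 1 to 1.5 months later, most likely on product, and the shipping rules contradict that maximum delay

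*Protocol*

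**What the plan says.** Four parts of the protocol bear on this.

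- **Start of intake (2.3).** "They are instructed to only start taking the collagen activator once the baseline assessment is completed". The clock is fixed by "Day 1 being the day of the baseline measurements", and "Follow up for the saliva test takes place +6 months from day 1".
- **Checking the sample (6.2 and 7.3).** "The samples are screened upon arrival at Trume labs and in the case that a sample is contaminated or too wet, we will be informed". Section 7.3 describes the check: on receipt "it undergoes a visual inspection to ensure it is not contaminated or too wet".
- **Replacing a rejected sample (6.2).** "it will be possible for the participant to redo the sample within 1 to 1.5 months maximum considering shipping times". The section bases this limit on weekly shipping and adds: "The delay of the datapoint will be taken into account for the analysis".
- **Shipping (3.3).** For the month-0 samples: "The study personnel will collectively ship the samples to Trume labs once all the baseline visits are completed". The month-6 samples are likewise held until all have been collected. Section 3.3 gives the month-6 sample a window of plus or minus one week.

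The primary objective (2.1) is the change in biological age from baseline over six months of intake. Saliva is taken only at months 0 and 6. The primary model in 4.1 has biological age reduction as the outcome and lists chronological age and sex as covariates.

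**The concern.** There is no control group, so each participant's month-0 saliva value is the only unexposed reference for the primary endpoint. The replacement rule does not separate month 0 from month 6. Applied at month 0, it puts a value taken after weeks of intake in place of that reference. For that person the contrast no longer measures six months against no exposure.

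The promise to account for the delay does not cure this. An exposed value can be turned back into an unexposed one only by assuming how the effect develops over time, and the protocol gives no such time course. The listed model has no term for sampling delay either.

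The stated maximum is also unreliable, because the two shipping descriptions cannot both be true. At month 6 the same rule produces a different fault: a retake falls outside the protocol's own window.

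**Working it through.** **Inputs.** Retake delay m = 1 to 1.5 months (6.2). Exposure period 6 months from day 1 (2.1, 2.3). One-sided alpha 0.05, effect size 0.5, n = 50, drop-out 15% to 20%, 60 enrolled (4.1). Rejection rate: not given, so the share k of participants with a replaced baseline is assumed to be 2% to 20%.

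**1. Is the retake on product?** Sections 2.3, 6.2 and 7.3 give this order: baseline visit on day 1, intake permitted, shipment, inspection abroad, notice of rejection, retake. No section ties intake to laboratory acceptance. A participant who follows the protocol is then about m months into intake at the retake.

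**2. Loss for an affected participant.** Share of exposure before the supposed baseline: f = m/6.

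- m = 1: f = 1/6 = 17%, leaving 5 months.
- m = 1.5: f = 1.5/6 = 25%, leaving 4.5 months.

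The same share of the effect is lost only if the effect builds linearly.

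**3. The stated maximum.** The protocol gives no transit or screening times, so 1 to 1.5 months cannot be rebuilt from its parts. It rests on a wait for dispatch of at most one week. Under batch shipping that wait runs up to the length L of the baseline phase, so the delay can reach roughly m + L. L is not stated. Section 3.3 has recruitment starting in August and the latest follow-up visit in December or January. If that means the month-3 clinic visit, the last baseline falls in September or October, so L is about 1 to 2 months (an inference). For the earliest participants:

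- L = 1: delay up to 2 to 2.5 months, f = 33% to 42%.
- L = 2: delay up to 3 to 3.5 months, f = 50% to 58%.

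**4. Effect on the trial mean (linear effect assumed).** Share retained = 1 − k × f.

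- k = 2%, m = 1: 1 − 0.02 × 0.167 = 0.997, a shrinkage of 0.3%.
- k = 20%, m = 1.5: 1 − 0.20 × 0.25 = 0.95, a shrinkage of 5%.

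These figures take the 1.5-month maximum as true. If batch shipping applied with L = 2 and visits evenly spread, the mean extra wait would be up to 1 month, and k = 20% would give up to 0.20 × 2/6 = 6.7% to 0.20 × 2.5/6 = 8.3%.

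**5. Effect on power.** The plan's n = 50 reproduces as the per-group size of a two-sample one-sided test (50.15). Inflating it gives 50/0.85 = 59 and 50/0.80 = 63, as stated. The comparison here is within participants. A paired one-sided test needs 27 (26.1 rounded up), and 50 give it 96.7% power. That mismatch is a separate matter, but it explains the reserve. With the shrinkage in step 4, power is 96.6% at the mild end (0.3%) and 95.2% at the severe end (5%).

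**6. Month 6.** A retake falls at 6 + 1 = 7 to 6 + 1.5 = 7.5 months, against a window of plus or minus one week. It may also fall after the six-month purchase is used up.

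**The case against.** The strongest case against the point has four parts.

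- **The effect is small, and its direction is cautious.** Rejections may be rare. A late baseline makes the observed change smaller if the product lowers biological age, and with no product effect exposure creates no false benefit. This stands, and it limits the weight of the point.
- **The analysis detail may belong in an analysis plan.** The promise to account for the delay could be met by exclusion, and the complete-case rule in 4.2 could drop a person without a valid baseline. This stands in part: the missing delay term alone is a weak complaint. But 6.2 fixes a procedure for replacing a sample, and nothing says that a replacement taken after first intake is not a baseline.
- **The on-product status is inferred.** One could read the baseline assessment as incomplete until the sample is accepted. No section says so, and counting day 1 and the follow-up visits from the baseline measurements speaks against it. It remains an inference, hence most likely rather than certain.
- **The clinic check is partial.** It does not reach the month-6 sample, which is collected at home, or damage in storage and shipping. This stands.

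A reader might also infer more than the documents support:

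- That the delay is unlimited under batch shipping. It is limited by the baseline phase plus turnaround.
- That an early effect would be lost altogether. No time course is given.
- That a late month-6 retake is off treatment. Participants buy six months of product, but nothing says that intake ends there.

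**Conclusion.** The point holds in a limited form. As written, the replacement rule admits a month-0 value that is most likely on product. For such a participant, 17% to 25% of the exposure period precedes the supposed baseline, and more for early participants if baseline samples are shipped in one batch. The conflict between 3.3 and 6.2 on shipping is plain on the page and needs correcting whatever the rejection rate.

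Across the trial the effect is probably small: about 0.3% to 5% off the mean effect and at most about 1.5 points of power (96.7% to 95.2%). This rests on an assumed 2% to 20% of replaced baselines, a linear effect, and a 1.5-month limit that is kept. A reader might infer that the primary result as a whole is compromised. The documents do not support that, since they give neither a rejection rate nor a time course. The fault lies in the validity of individual baselines and in a delay limit that the protocol itself contradicts. It should be corrected, and that is cheap.

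**What to change.** 1. **Shipping.** Reconcile 3.3 with 6.2 for both the month-0 and the month-6 samples, so that one schedule applies and the stated maximum delay is true under it.
2. **Baseline visit.** The laboratory's check is visual and clinic staff already look after the 45-minute drying. Have them apply the laboratory's criteria to the dried card and, if it fails, repeat the collection at that visit, before intake starts. Alternatively, keep a spare card from a separate collection. A second card from the same collection would share any contamination.
3. **Analysis rule.** State that a month-0 sample taken after first intake does not count as baseline in the primary analysis. Use such samples, and month-6 retakes outside the window, only in a sensitivity analysis with actual sampling dates.

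**Cost.** A short checklist or one spare card per participant. Because visits last 30 to 60 minutes and drying takes 45, some participants would have to stay longer for the check; the spare card avoids that. A few participants may leave the primary set. Even if 20% did, 60 enrolled with 15% to 20% drop-out leaves 51 to 48, and 80% of those is about 41 to 38, still above the 27 that a paired test needs under the plan's assumptions. Neither measure protects the month-6 home sample or prevents damage after the visit, so the third step is needed in any case.

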6.3 Rationale for the inclusion of vulnerable participants

This project will not be conducted in a vulnerable population.

7. Quality CONTROL AND Data protection

7.1 Quality measures

For quality assurance the Ethics Committee may visit the research sites. Direct access to the source data and all project related files and documents will be granted on such occasions.

Double data entry: Where possible, data will be entered twice by two different individuals to ensure accuracy and completeness. Any discrepancies between the two entries can be identified and resolved.

Project personnel training: Project personnel will be trained on all important project-related aspects, including data collection procedures, ethical guidelines, and quality control procedures. This will help ensure consistency and standardization across the project.

Planned quality visits: Planned quality visits will be scheduled to monitor the project's progress and identify any potential issues or areas for improvement. This will help ensure that the project is progressing according to plan and that data quality is maintained.

Independent data review: An independent data review can be conducted by an external expert or consultant to ensure that the data collected and analyzed is accurate and of high quality. This can provide an objective assessment of the project's strengths and weaknesses. Data quality checks: Data quality checks will be conducted periodically to ensure that the data collected is accurate and complete. This will involve checking for missing data, outliers, and data inconsistencies.

7.2 Data recording and source data

All the study data will be recorded via an electronic Case Report Form (eCRF) in Redcap. Data quality checks will be conducted periodically to ensure that the data collected in the eCRF is accurate and complete. This will involve checking for missing data, outliers, and data inconsistencies. To ensure data traceability, we will implement an audit trail to track any changes made to the data and who made them. Any discrepancies or errors will be documented and investigated immediately. Additionally, all research personnel involved in data collection, storage, and analysis will receive training on data protection and confidentiality.

Where possible, data is directly entered into redcap, also the questionnaires performed by the participants. At the clinic, there is the possibility that the readouts are first safed in the internal systems and then transferred to redcap, these records will be stored in a secure place at the clinic.

7.3 Confidentiality and coding

Project data will be handled with uttermost discretion and is only accessible to authorized personnel who require the data to fulfill their duties within the scope of the research project. On the CRFs and other project specific documents, participants are only identified by a unique participant number.

For our study, we will be using coded non-genetic data, as well as biological material that will be analyzed for genetic data and will also be coded. The participant identification list will be stored separately from the research data by Hautwerk, and will only be accessible to authorized personnel with specific permissions. All data will be stored on secure servers and protected by passwords, encryption, and other security measures to prevent unauthorized access, alteration, deletion, copying, and theft. We will also have safety backups of all data on secure storage media to ensure that data is not lost.

To ensure traceability, we will implement an audit trail to track any changes made to the data and who made them. Any discrepancies or errors will be documented and investigated immediately. Additionally, all research personnel involved in data collection, storage, and analysis will receive training on data protection and confidentiality.

Biological material in this project is not identified by participant name but by a unique participant number (code). Biological material is appropriately stored in a restricted area only

accessible to authorized personnel. All biological samples are analyzed by TruMe labs. The encrypting of the saliva samples is already performed at the Hautwerk clinic; specifically, the code of each saliva sample kit (6 digits) is noted down for the participant using the specific kit by the study doctor in the case report from. The rest of the study team will then only see the unique participant number and the allocated code of the saliva sample kit. For the analysis by TruMe laboratories, only the unique participant number will be used to identify whom the sample belongs to. Therefore, it is not possible for TruMe laboratories to identify a participant and they do not receive any identifying information apart from the unique participant number.

Measures taken to prevent unauthorized or accidental disclosure and to prevent the biological material from being altered, destroyed, or stolen at TruMe Laboratories:

- Upon receiving the sample, it undergoes a visual inspection to ensure it is not contaminated or too wet.
- If the sample passes the visual inspection, DNA extraction and bisulfite conversion are performed to differentiate the methylated and unmethylated DNA.
- Small regions of DNA are extracted and sequenced to quantify a percentage of DNA methylation.
- Independent laboratory services are used to perform all sequencing procedures.
- Personally identifiable information is not provided to TruMe, they only receive encrypted information to ensure confidentiality.
- Multiple layers of encryption are used to protect the data.
- TruMe never provides your information to your employer or health insurance company.
- Individual-level information is not shared with any third party without explicit consent.
- Information is only provided to law enforcement if required to comply with a valid subpoena or court-ordered request.

Processes in place to ensure traceability of biological material:

- Upon receiving the sample, it is scanned into an internal registration system.
- The laboratory sends the resulting data to TruMe along with the barcode that came with the sample.

• TruMe does not receive personal identifiable information for participants of this study. Storage and technical requirements to be met:

• The laboratory maintains a cooling system to ensure appropriate storage of biological material.

Shipping biological material or data collected during the research project outside the research site:

- the receiver address: TruMe, Inc., [name]
- responsible person to whom materials or data are sent: [name]
- purpose of shipment: Analysis of saliva samples to get biological age
- temperature control: not necessary, stable at ambient temperatures
- participant confidentiality is guaranteed via separating Personally identifiable information (PII) and personal health information (PHI).
- Participants are being sufficiently informed and consent is obtained that their biological material is being sent to the US to the contracted laboratory (Trume labs) that performes the analysis of the saliva samples.

The decision to conduct these analyses in the USA is rooted in a combination of scientific precedent and practical considerations. In a previous study²¹ that utilized the same company and testing method for analyzing biological age, remarkable outcomes were observed. This study indicated an average reduction of 8 years in biological age after an average of 7 months, and notably, the supplement used also contained alpha-ketoglutarate. Given this promising precedent, we aim to replicate these impressive results in our current study, maintaining consistency with the methods that led to such a meaningful outcome previously.

Furthermore, we've also considered the availability of alternative options within Switzerland. While ensuring local analysis is desirable, unfortunately, there are no local competitors who offer similar analyses at a cost comparable to the arrangement we have with our current US-based partner. Budget constraints are a significant consideration for our study, and partnering with the US-based company allows us to achieve comprehensive and high-quality analyses without compromising the study's financial scope.

Swiss dataprotection regulations upheld in the US:

- All saliva samples sent to the US laboratory are encoded using encryption protocols, which adhere to both Swiss Federal Data Protection Act (FADP) and US data security standards. This step ensures that the genetic material remains secure and unreadable during transmission and analysis, minimizing the risk of unauthorized access.
- As the scope of analysis is limited to only 9 short gene sequences directly relevant to determining biological age, this focused approach ensures that only the necessary genetic information is utilized, in alignment with Swiss data protection principles of data minimization. Once this analysis is completed and the biological age is determined, the genetic information used for this specific purpose is promptly deleted. This precautionary measure adheres to both Swiss and US regulations and minimizes the retention of sensitive information to what is strictly essential.
- Throughout the entire process, the US laboratory conducting the analysis does not have access to any identifying information linked to the samples. This includes personal details of the participants or any contextual information. The encrypted data ensures that the laboratory lacks the capacity to link the samples to specific individuals, thereby preserving the anonymity of participants.
- Further, strict access controls are in place at TruMe laboratories. Only authorized personnel directly involved in the analysis process have limited access to the encrypted genetic data. This controlled access ensures that information is handled responsibly and with the utmost care.
- From each participant informed consent will be obtained and they are informed about the details of the analysis and that it is taking place in the US. This transparent communication ensures that participants are aware of the process and can make an informed decision about their participation, in alignment with Swiss data protection guidelines. Further, they are informed that withdrawal of the study is possible at any time and without reason.

